6.2. Subject Exclusion Criteria

The presence of any of the following will exclude a subject from study enrollment:

- 1. Any of the following in the past 6 months: myocardial infarction, uncontrolled cardiac arrhythmia, unstable angina, coronary/peripheral artery bypass graft, symptomatic congestive heart failure, cerebrovascular accident or transient ischemic attack, pulmonary embolism, deep vein thrombosis.
- 2. Grade >1 retinopathy as determined by an ophthalmologist.
- 3. Known brain metastases.
- 4. Major surgery, other than diagnostic surgery, within 4 weeks prior to treatment.
- 5. Active, uncontrolled bacterial, viral, or fungal infections.
- 6. Known infection with HIV, active hepatitis B or hepatitis C.
- 7. Pregnant or breast feeding women.
- 8. Previous (within the last 5 years) or current malignancies at other sites, except for adequately treated basal cell or squamous cell skin cancer or in situ carcinoma of the cervix uteri.
- 9. Current enrollment in or participation in another therapeutic clinical trial within 4 weeks preceding treatment start.
- 10. Diabetes mellitus uncontrolled.
- 11. Gastrointestinal disease (e.g. Crohn's disease, ulcerative colitis, or short gut syndrome) that would impact on drug absorption.
- 12. Patients under treatment with anticoagulants or with coagulation disorders or with signs of hemorrhage at baseline.
- 13. Patients with previous history or current presence of neurological disorders, including epilepsy (although controlled by anticonvulsant therapy), Parkinson's disease and extra-pyramidal syndromes.
- 14. Other severe acute or chronic medical or psychiatric condition or laboratory abnormality that may increase the risk associated with study participation or may interfere with the interpretation of study results and, in the judgment of the Investigator, would make the patient inappropriate for entry into this study or could compromise protocol objectives in the opinion of the Investigator and/or the Sponsor.

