9.4.8. Assessment of Potential Ocular Toxicity

Ocular toxicity has been reported in rats treated for prolonged period of time (daily treatments for 3 consecutive weeks + 1 week of rest x 3 cycles or daily treatments for 4 consecutive weeks) at doses associated with daily AUCs close to 25 μ M·h, as well as in rats given daily treatments for 2 consecutive weeks +1 week of rest for 5 cycles at doses associated to AUC of about 32 μ M·h.

No ocular toxicity was observed in rats with a 7-day repeat treatment schedule up to doses associated to a daily AUC of about 50μ M·h or up to doses associated to a daily AUC of about 10 μ M·h in the 4-week schedule and up to doses associated to daily AUC of about 12 μ M·h. in the 3-week schedule.

Tiziana Life Sciences, PLC - Confidential Page 53 of 101

Milciclib maleate (PHA-848125AC)	CDKO-125a-006-P4
Protocol for Study CDKO-125a-006	09 March 2017

Despite clinical manifestations of ocular toxicity were not observed in the clinical studies so far, a potential ocular toxicity cannot be excluded. During visits, patients treated with PHA-848125AC will undergo regular clinical examinations, i.e. ophthalmologic examination (visual acuity test and funduscopic examination), at the end of even cycles (see Schedule of Events in Section 7 and also Section 11.4.3).

Retinopathy will be graded according to NCI CTCAE version 3.0 grading system as follows:

Reti	nopathy Grades, NCI CTCAE Version 3.0
0.	Absent
1.	Asymptomatic
2.	Symptomatic with moderate decrease in visual acuity (20/40 or better)
3.	Symptomatic with marked decrease in visual acuity (worse than 20/40)
4.	Blindness (20/200 or worse)

Grade 1 retinopathy is allowed at study entry since it is an asymptomatic event occurring in relation to common medical conditions such as hypertension [37,38]. It is recognized that several patients in their 50s and 60s with underlying hypertension may present asymptomatic retinopathy. Such a status is to be regarded as a condition which does not prevent patients' enrollment in the study, being not clinically significant.

Ophtalmologic evaluations will be possibly done by the same ophthalmologist for a given patient.

The increase of 1 or more grades retinopathy by ophthalmologic examination will require immediate study drug discontinuation.

Management of ocular adverse events should refer to institutional interventional protocols.

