Laboratory test values will be graded according to the NCI CTCAE scale, v3.0, whenever possible. For each laboratory test included in the NCI CTCAE system, the incidence of Tiziana Life Sciences, PLC - Confidential Page 78 of 101 abnormalities will be evaluated by considering the worst occurrence for each patient throughout the whole treatment period. The frequency distributions of cycles according to the worst CTCAE grade will also be calculated for selected parameters, as clinically indicated. Preliminary conversions of reported values from the originally reported units to a set of predefined units will be applied to facilitate the comparison. For selected parameters descriptive analysis of shifts relative to baseline will be performed if deemed of clinical relevance. Coagulation tests will be evaluated with respect to the corresponding baseline values and to the recorded normal ranges. Urinary parameters will be documented in patient data listings.

Ophthalmologic examinations will be summarized in terms of normal / abnormal findings. Shift tables comparing patients' worst assessments after treatment initiation to the corresponding baseline assessments will be built.

All collected safety data (including vital signs, ECG, ophthalmologic evaluations, laboratory tests and adverse events) will be presented in individual patients' data listings. Identification of clinically relevant values and calculation of changes from baseline will be provided in the listings for those parameters and conditions deemed of clinical relevance.

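### The ophthalmologic shift table in Protocol Section 12.3.6, read on its normal/abnormal scale, cannot display the protocol's own ocular event, a rise of one or more retinopathy grades from baseline

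*Protocol*

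**What the plan says.** Ophthalmologic examination is a named component of the secondary safety endpoint in Protocol Section 4.2.2. Section 12.3.6 fixes how it is summarised: "Ophthalmologic examinations will be summarized in terms of normal / abnormal findings". The next sentence adds: "Shift tables comparing patients' worst assessments after treatment initiation to the corresponding baseline assessments will be built". No grade or other category is named for that table.

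Elsewhere the protocol works with grades. Section 9.4.8 says: "Retinopathy will be graded according to NCI CTCAE version 3.0 grading system as follows", and lists grades 0 to 4, where grade 1 is asymptomatic, grades 2 and 3 are symptomatic with increasing loss of acuity, and grade 4 is blindness. Exclusion criterion 2 in Section 6.2 bars only "Grade >1 retinopathy as determined by an ophthalmologist". Section 9.4.8 gives the reason: "Grade 1 retinopathy is allowed at study entry since it is an asymptomatic event occurring in relation to common medical conditions such as hypertension". It also expects such patients: "It is recognized that several patients in their 50s and 60s with underlying hypertension may present asymptomatic retinopathy".

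The event on which the protocol acts is a change in grade: "The increase of 1 or more grades retinopathy by ophthalmologic examination will require immediate study drug discontinuation". Table 4 in Section 9.4.3 has the same rule and states that the comparison is with baseline.

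**The concern.** The examinations are graded on a five-level scale and acted upon by change in grade, but the analysis section reduces them to two levels. The entry rule makes this matter, because some patients can start in the abnormal category. A patient who is abnormal at baseline has no worse category to move to, so further worsening looks the same as no change. For a patient who starts normal, the table shows that something happened but not whether it was an asymptomatic finding or blindness.

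At stake is whether the one planned aggregate baseline comparison for these dedicated examinations can answer the question the protocol itself asks: how many patients had a rise of one or more retinopathy grades?

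**Working it through.** The plan gives no figure to reproduce. The check enumerates which worsening transitions the table can show.

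**Inputs**
- Possible baseline grades: 0 or 1 (Section 6.2, exclusion 2; Section 9.4.8).
- Possible worst post-baseline grades: 0 to 4 (Section 9.4.8).
- Event of interest: worst grade minus baseline grade of at least 1 (Section 9.4.8; Table 4).
- Scale of the summary: normal or abnormal (Section 12.3.6).
- Assumption on coding: grade 0 is normal and grade 1 or more is abnormal. The protocol does not define the two words.
- Assumption on the table: the shift table uses the scale of the sentence before it.

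**Number of worsening transitions.** From grade 0 there are 4 (to 1, 2, 3, 4). From grade 1 there are 3 (to 2, 3, 4). Total: 4 + 3 = 7.

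**Where each falls**

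| Transition | Cell in a normal/abnormal table | Seen as worsening? | Severity shown? |
|---|---|---|---|
| 0 to 1 | normal to abnormal | yes | no |
| 0 to 2 | normal to abnormal | yes | no |
| 0 to 3 | normal to abnormal | yes | no |
| 0 to 4 | normal to abnormal | yes | no |
| 1 to 2 | abnormal to abnormal | no | no |
| 1 to 3 | abnormal to abnormal | no | no |
| 1 to 4 | abnormal to abnormal | no | no |

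So 4 of 7 transitions are visible and 3 of 7 are not. The three that are lost are all of those open to a patient who enters with grade 1, and they share their cell with patients who stay at grade 1. The four that are visible all share one cell.

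**Same enumeration with a graded table.** With baseline grade (0 or 1) in rows and worst grade (0 to 4) in columns, all 7 transitions lie off the diagonal, each in its own cell. The protocol's event is the sum of those 7 cells.

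**Sensitivity to the coding assumption.** Suppose grade 1 is coded normal and only grade 2 or more is abnormal. Then 0 to 2, 3, 4 and 1 to 2, 3, 4 are visible (3 + 3 = 6), but 0 to 1 falls in the normal-to-normal cell. That is 6 of 7, and the missing transition is also a one-grade rise under Section 9.4.8. Under either coding, the two-level table does not count the protocol's event.

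**Patients affected.** This would be the number entering with grade 1 multiplied by the proportion of them who worsen. The protocol gives neither quantity, so no count can be derived.

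**The case against.** The strongest reply is that the worsening is captured elsewhere, and by grade. Section 11.4.1.1.1 counts worsening of a pre-existing abnormality as an adverse event. Grades 2 to 4 are symptomatic by the protocol's own scale, so every worsening from grade 1 is symptomatic. Section 12.3.6 tabulates adverse events per patient by worst CTCAE grade, with separate subsets for grades 3 to 5 and for events leading to discontinuation. Because a one-grade rise requires discontinuation, such a patient should also appear in the reasons for stopping treatment (Section 12.3.1). Individual ophthalmologic data are listed.

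This stands and sets the size of the point. A reader might infer that ocular safety as a whole will look better than it is. The document does not support that, because the loss is confined to one table. What the other outputs do not give is a tabulated change from baseline: in a worst-grade table, 0 to 2 and 1 to 2 look the same, and listings are not a summary.

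A second reply is that the shift-table sentence does not itself say normal/abnormal, that abnormal is undefined, and that Section 9.4.8 treats grade 1 as clinically unimportant. This is fair, and a reader should not take the two-level shift table as stated outright. It is the natural reading, since the sentence directly follows the two-level summary and names no alternative. Coding grade 1 as normal moves the blind spot without removing it.

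A third reply is that the rat finding is remote from this schedule. Section 3.2.5 reports retinal atrophy that did not regress after dosing for a month or more, but no retinal change after 7 consecutive days up to a daily AUC of about 50 µM·h; Section 3.2.7 gives a mean of 25.3 µM·h at the study dose. That lowers the expected number of events. It does not alter what the table can show, and Section 9.4.8 itself keeps the risk open.

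Finally, the examination also covers visual acuity, so a common normal/abnormal summary has a use. The fix keeps it for findings other than retinopathy.

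**Conclusion.** The point holds as a minor one. On the natural reading of Section 12.3.6, and with grade 1 coded abnormal, the table hides 3 of the 7 possible worsening transitions and merges the other 4 in one cell, so it cannot display an increase of one or more grades from baseline. This rests on two assumptions that the protocol does not settle: that the shift table uses the normal/abnormal scale, and that grade 1 counts as abnormal.

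No number of affected patients should be attached. Section 9.4.8 says only that several patients may have asymptomatic retinopathy; any percentage would be a guess, and a count of patients with baseline findings would not be a count of patients whose worsening is lost.

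Nor is this merely detail left to a statistical analysis plan. The protocol states a scale for the examinations, and a plan written to follow it would carry the loss forward.

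**What to change.** In Section 12.3.6, replace the two-level shift for retinopathy with a table of baseline by worst post-baseline CTCAE v3.0 retinopathy grade (0 to 4). Report beside it the number and percentage of patients with an increase of one or more grades. Keep normal/abnormal for the other ocular findings.

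The baseline and on-treatment grades are already needed to apply Section 9.4.8 and Table 4, so no new examination is required and no clinical rule changes. The cost is one table, on condition that the grade is recorded on the CRF at each examination. Section 9.4.8 says that retinopathy will be graded but does not say where the grade is recorded, so that should be confirmed first.

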12.3.7. Analyses of Other Endpoints

12.3.7.1. Baseline Expression of Molecular Markers in Tumor Biopsies

The collection of these data is foreseen only in the consenting patients with available tumor samples.

Descriptive statistics of molecular features of p53, p21, p27, cyclin D1, p75, TRKA and other genes/proteins involved in the PHA-84125AC mechanism of action in the available tumor samples will be presented. Exploratory analyses on the relationship between these markers and treatment efficacy variables (e.g. PFS-3, PFS, objective tumor response, OS) will be performed only if sufficient data are collected.

12.3.7.2. Pharmacokinetics

Plasma levels versus sampling times will be presented in tabular and graphic form, if applicable.

12.3.7.3. Concomitant Medications and Post-Treatment Anti-tumor Therapies

Individual patients' data listings will be prepared to document the administration of concomitant medications.

Patients starting antitumor therapies during follow-up will be identified in a patients' data listing.

Tiziana Life Sciences, PLC - Confidential Page 79 of 101

12.4. Interim Analysis Plan

Not Applicable in this study.

12.5. Data Monitoring Committee

Not applicable.

13. END OF STUDY

After approval of Amendment 4, the end of the trial is defined as the last visit of the last patient, occurring when all patients have discontinued study therapy.

14. QUALITY CONTROL AND QUALITY ASSURANCE

Monitoring visits to the trial site will be made periodically during the trial to ensure that GCPs and all aspects of the protocol are followed. Source documents will be reviewed for verification of agreement with data on case report forms. The investigator/institution guarantees direct access to source documents by the Sponsor and appropriate regulatory authorities.

The trial site may also be subject to review by the institutional review board (IRB)/independent ethics committee (IEC) to quality assurance audits performed by the Sponsor, and/or to inspection by appropriate regulatory authorities to assure compliance with proper trial conduct.

It is important that the investigator(s) and their relevant personnel are available during the monitoring visits and possible audits or inspections and that sufficient time is devoted to the process

15. DATA HANDLING AND RECORD KEEPING

15.1. Case Report Forms

A case report form is required and should be completed for each included subject. The completed original case report forms are the sole property of Tiziana Life Sciences, PLC and should not be made available in any form to third parties, except for authorized representatives of appropriate regulatory authorities, without written permission from Tiziana Life Sciences.

It is the investigator's responsibility to ensure completion and to review and approve all case report forms. Case report forms must be signed by the investigator or by an authorized staff member. These signatures serve to attest that the information contained on the case report forms is true. At all times, the investigator has final personal responsibility for the accuracy and authenticity of all clinical and laboratory data entered on the case report forms. Subject

Tiziana Life Sciences, PLC - Confidential Page 80 of 101

Milciclib maleate (PHA-848125AC)	CDKO-125a-006-P4
Protocol for Study CDKO-125a-006	09 March 2017

source documents are the physician's subject records maintained at the study site. In most cases, the source documents will be the hospital's or the physician's chart. In cases where the source documents are the hospital or the physician's chart, the information collected on the case report forms must match those charts. In some cases, a portion of the source documents for a given study/site may be the case report forms. The investigator must agree which items will be recorded in the source documents and for which items the case report form will stand as the source document.

For patients still on treatment at the cut-off date of 31 May 2017, data should be recorded only in the patient's medical notes.

15.2. Record Retention

To enable evaluations and/or audits from regulatory authorities or Tiziana Life Sciences, PLC, the investigator agrees to keep records, including the identity of all participating subjects (sufficient information to link records, case report forms and hospital records), all original signed informed consent forms, copies of all case report forms, source documents, and detailed records of treatment disposition. The records should be retained by the investigator according to local regulations or as specified in the Clinical Trial Agreement, whichever is longer.

If the investigator relocates, retires, or for any reason withdraws from the study, the Sponsor should be prospectively notified. The study records must be transferred to an acceptable designee, such as another investigator, another institution, or to Tiziana Life sciences, PLC. The investigator must obtain the Sponsor written permission before disposing of any records.

For patients still on treatment at the cut-off date of 31 May 2017, data should be recorded only in the patient's medical notes.

16. ETHICS

16.1. Institutional Review Board (IRB)/Independent Ethics Committee (IEC)

Approval of the trial protocol, protocol amendments, informed consent forms, and other relevant documents (eg, advertisements), if applicable, must be obtained from the IRB/IEC according to applicable regulatory requirements.

The only circumstance in which an amendment may be initiated prior to IRB/IEC approval is where the change is necessary to eliminate apparent immediate hazards to the subjects. In that event, the investigator must notify the IRB/IEC and the local Nerviano Medical Sciences site personnel as soon as the change has been implemented.

Tiziana Life Sciences, PLC - Confidential Page 81 of 101

16.2. Ethical Conduct of the Trial

The trial will be performed in accordance with International Conference on Harmonization Good Clinical Practice guidelines, the Declaration of Helsinki (1996 Version), and applicable local regulatory requirements and laws.

16.3. Subject Information and Consent

It is the responsibility of the Investigator to give each subject (or the subject's acceptable representative) full and adequate verbal and written information regarding the objective and procedures of the trial and the possible risks involved. This information must be provided to the subject prior to undertaking any trial-related procedure. The subjects must be informed about their right to withdraw from the trial at any time. Written subject information, approved by the IRB/IEC, must be given to each subject before any trial-related procedure is undertaken. The written subject information must not be changed without prior approval by NMS and the IRB/IEC. Furthermore, it is the responsibility of the Investigator to obtain signed and dated informed consent from all subjects, and a signature from the persons conducting the informed consent discussion, prior to undertaking any trial-related procedure.

A recommended informed consent sample is provided in Appendix 1 of this protocol.

17. SPONSOR DISCONTINUATION CRITERIA

Tiziana Life Sciences, PLC reserves the right to discontinue the trial prior to inclusion of the intended number of subjects, but intends only to exercise this right for valid scientific or administrative reasons. After such a decision, the Investigator must contact all participating subjects within a time period set by the Sponsor. In any case, for patients on treatment, the Sponsor will guarantee the supply of PHA-848125AC until the patients will benefit from this product. As directed by the Sponsor, all study materials must be collected and all case report forms completed to the greatest extent possible.

18. DISSEMINATION AND PUBLICATION OF RESULTS

The conditions regulating dissemination of the information derived from this clinical study are described in the Clinical Trial Agreement. Presentations, abstracts, publications of the study results are to be submitted to the Sponsor for internal review procedure, at least 1 month before submission.

2 Clavicles	21.6	0.75	16.2	
Sternum	39.0	0.6	23.4	2.3
Ribs			82.6	7.9
1 pair	10.2	All 0.4	4.1	
2	12.6		5.0	
3	16.0		6.4	
4	18.6		7.4	
5	23.8		9.5	
6	23.6		94	
7	25.0		10.0	
8	24.0		9.6	
9	21.2		8.5	
10	16.0		64	
11	11.2		4 5	
12	4.6		1.8	
Vertebrae (Cervical)			35.8	3.4
	6.6	All 0 75	5.0	
2	84	1111 0.70	63	
3	5.4		41	
4	5.7		43	
5	5.8		4 4	
6	7.0		53	
7	8.5		6.4	
Vertebrae (Thoracic)			147.9	14.1
1 pair	10.8	All 0 75	81	
2	11.7	1111 0.70	8.8	
$\frac{-}{3}$	11.4		8.5	
4	12.2		91	
5	13.4		10.1	
6	15.3		11.5	
7	16.1		12.1	
8	18.5		13.9	
9	19.7		14.8	
10	21.2		15.9	
11	21.7		16.3	
12	25.0		18.8	

The distribution of bone marrow in the adult

Tiziana Life Sciences, PLC - Confidential Page 100 of 101

Site	Marrow	Fraction Red	Red Marrow	% Total Red
	Weight (g)	Marrow - Age 40	Weight -Age 40 (g)	Marrow
Vertebrae (Lumbar)			114.1	10.9
1 pair	27.8	All 0.75	20.8	
2	29.1		21.8	
3	31.8		23.8	
4	32.1		24.1	
5	31.4		23.6	
Sacrum	194.0	0.75	145.6	13.9
Lower limb girdle			273.0	26.1
2 os coxae	310.6	0.75	233.0	
2 femoral head & neck	53.0	0.75	40.0	
Total	1497.7		1045.7	100.0

The distribution of bone marrow in the adult

R.E. ELLIS - The Distribution of Active Bone Marrow in the Adult. Phy. Med. Biol. 5, 255 - 258, 1961

Tiziana Life Sciences, PLC - Confidential Page 101 of 101
